4.1.5 Blinding and procedures for unblinding

4.1.5.1 Blinding

This is an open-label study. Due to the safety obligation in this paediatric setting, the trial will be conducted in an unblinded fashion to ensure a rigorous supervision of the study. Investigators, patients, and trial members will be unblinded. The only party blinded to treatment assignment are members of the adjudication committee.

Proprietary confidential information.

© 2019 Boehringer Ingelheim International GmbH or one or more of its affiliated companies. All rights reserved.

This document may not - in full or in part - be passed on, reproduced, published or otherwise used without prior written permission.

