3.1.1.2 Central Independent Blinded Adjudication Committee

All components of the primary efficacy endpoint as well as all bleeding and all fatal events will be centrally adjudicated by an independent adjudication committee that will be blinded to all treatment assignments and will confirm or refute outcome events.

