5. VARIABLES AND THEIR ASSESSMENT

5.1 EFFICACY - PHARMACODYNAMICS

5.1.1 Endpoints of efficacy

Primary endpoint:

Efficacy combined endpoint Proportion of patients with:

- Complete thrombus resolution and;
- Freedom from recurrent VTE (including symptomatic and asymptomatic, contiguous progression or non-contiguous new thrombus, deep vein thrombosis, pulmonary and paradoxical embolism, thrombus progression) and;
- Freedom from mortality related to VTE.

The events outlined in the above combined primary endpoint will be assessed by radiologists or other such qualified clinicians using an appropriate method such as ultrasound, echocardiography, venography or computed tomography (CT scan) based on the location of the thrombus and the test used to perform the baseline assessment.

All components of the primary efficacy endpoint as well as all bleeding and all fatal events will be centrally adjudicated by an independent blinded committee.

Secondary endpoints:

- Freedom from major bleeding events (MBEs), defined as either fatal bleeding; clinically overt bleeding associated with a decrease in haemoglobin of at least 20 g/L in a 24-hour period; bleeding that is retroperitoneal, pulmonary, intracranial or otherwise involves the central nervous system; or bleeding that requires intervention in an operating suite.
- Pharmacokinetic and pharmacodynamic assessments at visit 3 (after at least six consecutive dabigatran doses) and after at least 3 days following any dabigatran dose adjustment
- Frequency of dose adjustments (i.e. Number of subjects with dose adjustment), temporary and permanent discontinuation from therapy and number of subjects with laboratory monitoring requirements for dose adjustment during the treatment phase
- Frequency of switch of type of anti-coagulation therapy (including dabigatran to SOC) (Frequency of subjects switching the type of anti-coagulation therapy including dabigatran etexilate to standard of care and switching from an intended standard of care treatment to another)
- Freedom from thrombus progression at end of therapy (day 84 after randomisation (Visit 8) or eEOT whichever comes first) compared to baseline
- Assessment of the acceptability of an age-appropriate formulation at end of therapy
- All bleeding events

Proprietary confidential information.

© 2019 Boehringer Ingelheim International GmbH or one or more of its affiliated companies. All rights reserved.

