7.3.1 Primary analyses

The primary efficacy endpoint, proportion of patients with complete thrombus resolution and freedom from recurrent VTE or mortality related to VTE, will be analysed following the ITT principle on the randomized set. Age group will be used as stratification factor using a Mantel-Haenszel type weighted average of differences with weights as proposed by Greenland and Robins ([R09-1299](#)).

The primary analyses for primary endpoints will include only adjudicated events.

The planned analyses are summarized in Table 7.3.1: 1 for each population set. More details and additional analyses will be specified in TSAP if deemed necessary.

Table 7.3.1: 1 Summary of planned analyses

Population / analysis	Intent-to-treat analysis (from randomization to the time point of interest)	On-treatment analysis (from treatment start to drug stop date + 6 days)
Randomized set	1. Primary efficacy endpoint: primary and secondary analysis 2. Secondary efficacy endpoints 4. All cause mortality	
Treated set		1. Major bleeding events analysis 4. All cause mortality

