7.4 PRIMARY ENDPOINTS

Primary analysis

The primary analysis of the primary efficacy endpoint will be performed on the randomized set following the intention-to-treat (ITT) principle, based on adjudicated data. For example: patients who were originally randomized to DE and later switched to SOC before Day 84, as cases of premature termination of the study medication, will be further followed up per the visit schedule until Day 84.

The analysis period in the primary analysis starts from the time of randomization to the time point of interest, that is, Day 84 \pm 7 days.

- For patients who die or withdraw consent prior to Day 84 – 7 days, the period for the primary analysis ends with the date of trial completion (i.e. the date of death, or the date of consent withdrawal).
- For patients who discontinue treatment prematurely (for example, due to complete thrombus resolution, AE, DE concentration out of target range after one dose modification, and so on), the latest available thrombus assessment up to Day 84 + 7 days will be used for the primary analysis. In particular, thrombus assessment performed after eEOT but before/at Visit 8 for patients switching from DE to SOC will be used for primary analysis. In terms of the recurrent VTE component or VTE-related mortality component, recurrence or death up to Day 84 + 7 days will be used for primary analysis.
- Patients who are still being treated and have not yet reached Day 84 \pm 7 days at time of EMA interim data cut-off will not be included in the analysis

The primary efficacy endpoint contains three components. Given the composite nature of the primary endpoint, each component will be evaluated separately, and a joint outcome of achieving the primary endpoint will be concluded only if all three components are satisfied.

Component 1: free from VTE-related mortality

Patients with VTE-related death occurring between randomization to Day 84 + 7 days will be considered as NOT meeting the endpoint in terms of the component of “freedom from mortality related to VTE”, and therefore will not contribute to the proportion of patients achieving the primary efficacy endpoint.

Component 2: free from recurrent VTE

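### The end-of-therapy clot image may be acquired and reported by someone who knows the arm, and blinded adjudication cannot remove bias already in that material

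*Protocol*

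**What the plan says.** The trial is open-label. Protocol 4.1.5.1 gives the safety obligation to children as the reason and states: "Investigators, patients, and trial members will be unblinded". It then adds: "The only party blinded to treatment assignment are members of the adjudication committee".

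Protocol 5.1.1 assigns the first assessment of the primary endpoint: "The events outlined in the above combined primary endpoint will be assessed by radiologists or other such qualified clinicians". The listed methods include ultrasound, echocardiography, venography and CT. Section 5.1.2.2 asks for the same method as at baseline when appropriate. It does not say whether the person performing or reporting the scan may know the treatment.

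Above that first assessment sits a real safeguard. Under Protocol 3.1.1.2 all components of the primary endpoint "will be centrally adjudicated by an independent adjudication committee that will be blinded to all treatment assignments and will confirm or refute outcome events". Protocol 7.3.1 adds: "The primary analyses for primary endpoints will include only adjudicated events". SAP 7.4 describes the primary analysis as "following the intention-to-treat (ITT) principle, based on adjudicated data".

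Protocol 8.3.1 has the site supply the committee with copies of the source documents needed, after removing patient identifiers. It does not say whether original images are included or whether treatment information is removed.

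**The concern.** Complete versus incomplete resolution is a threshold call, and it decides one of the three components of the primary endpoint. A masked committee removes bias from its own judgement. It cannot restore what was never recorded. With real-time ultrasound the operator chooses which segments to examine, which frames to keep and how hard to look for residual clot. If the operator or reporter knows the arm, that knowledge can shape the evidence before the committee sees it.

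The test compares about 94 dabigatran patients with about 47 on standard of care (SOC). A net shift of a few percentage points in one arm changes both the false-positive rate at the margin and the power. The shift could favour either arm.

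**Working it through.** **Inputs.** Protocol 7.6 gives 94 and 47 patients, a margin of 20 percentage points, an assumed rate of 72% in both arms, and a lower bound with multiplier 1.64. Two inputs are not in the documents and are assumed here:
- *b*, the share of clots in one arm misread in one direction. Values used: 5% and 10%.
- *c*, the share of those misreads that adjudication corrects. Values used: 0, 50%, 90% and 100%.

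**Method.** Non-inferiority is claimed when

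p̂(DE) − p̂(SOC) − 1.64 × √[p̂(DE)(1 − p̂(DE))/94 + p̂(SOC)(1 − p̂(SOC))/47] > −0.20.

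The probability of this is summed exactly over the two binomial distributions.

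**Step 1: reproduce Table 7.6: 2.**

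| True rates (DE, SOC) | Plan | Recomputed |
|---|---|---|
| 77%, 72% | 95% | 95.2% |
| 72%, 72% | 82% | 81.8% |
| 68%, 72% | 63% | 63.3% |
| 62%, 72% | 33% | 32.3% |
| 52%, 72% | 5% | 4.7% |

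The plan's figures are reproduced to within a percentage point.

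**Step 2: bias in favour of dabigatran, truth at the margin.** The dabigatran rate that reaches the analysis is 0.52 + 0.48 × b × (1 − c). SOC stays at 0.72.

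| b | c | Analysed DE rate | False-positive rate |
|---|---|---|---|
| 5% | 0 | 0.52 + 0.48 × 0.05 = 0.544 | 8.2% |
| 5% | 50% | 0.52 + 0.48 × 0.025 = 0.532 | 6.2% |
| 5% | 90% | 0.52 + 0.48 × 0.005 = 0.522 | 5.0% |
| 10% | 0 | 0.52 + 0.48 × 0.10 = 0.568 | 13.4% |
| 10% | 50% | 0.52 + 0.48 × 0.05 = 0.544 | 8.2% |
| 10% | 90% | 0.52 + 0.48 × 0.01 = 0.525 | 5.3% |
| any | 100% | 0.520 | 4.7% |

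**Step 3: bias against dabigatran, no correction.** Suppose 5% of resolved dabigatran clots are read as unresolved.
- True equality at 72%: the analysed rate is 0.72 × 0.95 = 0.684, and power falls from 81.8% to 65.4%.
- Truth at the margin: the analysed rate is 0.52 × 0.95 = 0.494, and the false-positive rate falls to 2.4%.

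**What this shows.** The result depends mainly on c, that is, on how far the committee's decision is independent of the site's acquisition and report. The documents do not describe this.

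**The case against.** The strongest objection is that the plan already has the standard protection for an open-label trial. Every component is decided by an independent committee blinded to treatment, and only those decisions enter the primary analysis. A reader might infer from 4.1.5.1 and 5.1.1 that the endpoint itself is read unblinded at the site. The documents do not support that: the site reading feeds the endpoint, and the committee's determination is what is analysed.

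A second objection is that silence about the committee's material does not show a defect. An adjudication charter, not among the documents, may require original images and masked packets. Nothing in the documents says that the committee relies on site reports, and no mix of imaging methods is given, so the weight of ultrasound is unknown. This stands as far as the packet is concerned. It does not settle the masking of whoever acquires the scan, which happens before the committee's work and which 4.1.5.1, as worded, does not provide for.

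Third, SAP 7.5.2 plans a concordance summary of adjudicated against investigator-reported events. That is useful, but if the committee depends on site evidence, agreement would be high whether or not that evidence is biased.

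Finally, a reader might infer that the false-positive rate is well above 5%. That does not follow. With 5% or 10% misreading in opposite directions in both arms and nothing corrected, the rate would be 17.0% or 40.1%. With 90% corrected, the same cases give 5.5% and 6.3%. The 40.1% case shrinks the apparent difference from 20 to about 8 points (0.648 − 0.568), which is not a small shift.

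**Conclusion.** The point holds as a limited gap in masking ahead of adjudication. The plan does not keep the arm from the person who acquires and reports the end-of-therapy image. Nor does it say that the committee receives original images or packets cleared of treatment information. Blinded adjudication reduces the resulting risk by an amount the documents do not allow us to estimate.

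Under the assumed misreading of 5% to 10% in one arm, the false-positive rate at the margin lies between 4.7% (all corrected) and 13.4% (none corrected). Misreading of 5% in the other direction, uncorrected, would cut power from 82% to 65%. These are illustrations of what is at stake, not estimates of bias, and neither the sample size nor the planned power needs to change. The case for acting is that the remedy costs little.

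**What to change.** 1. **Protocol 4.1.5.1 and 5.1.2.2.** State that planned index-thrombus imaging at Visit 8 and eEOT is, where feasible, requested, performed and reported by the usual site reader without the treatment arm. The request gives clot location, baseline image and method only. Investigators stay unblinded.
2. **Protocol 8.3.1.** State that the original baseline and end-of-therapy images go to the committee together with the site report. Treatment information (drug name, INR, anti-Xa, dabigatran level) is removed as well as patient identifiers. If a charter already says this, a reference to it is enough.

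**Cost.** A short text change in three sections and a new imaging request form. No extra reader, visit or scan. Masking cannot be guaranteed, because the family or the medical record may reveal the drug.

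Urgent unscheduled imaging is left as it is. Since SAP 7.4 can carry forward a scan from an unscheduled visit when the Day 84 assessment is missing, a few endpoint images may remain outside the masking.

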4.1.5.2 Procedures for emergency unblinding

Not applicable as this is an open-label study.

4.1.6 Packaging, labelling, and re-supply

For details of packaging and the description of the label, refer to the ISF.

4.1.7 Storage conditions

Patients/parents/legal guardians should be reminded to store and use LMWHs or VKAs or fondaparinux according to investigator instructions in consideration of local product labels.

Dabigatran should be kept out of the reach of children and be stored protected from moisture and direct sunlight. Dabigatran capsules should be kept in their supplied container and the bottle lid must be kept closed. Dabigatran capsules must not be transferred to other types of containers. The medication stick packs containing the dabigatran etexilate granules should be kept sealed until just prior to reconstitution. The medication stick packs containing the dabigatran etexilate pellets should be kept sealed until just prior to intake.

Patients/parents/legal guardians should be instructed to keep medication containers tightly closed and not to remove capsules from the original packaging material until immediately prior to the time of intake. Dabigatran may only be dispensed to trial patients fulfilling the inclusion and exclusion criteria by authorised study personnel as documented in the ISF. Receipt, usage, and return of the study medication must also be documented on the respective forms in the ISF. All unused medication including bottles and outer boxes (empty or filled) must be either returned to the sponsor, or, following written authorisation from the sponsor, may be destroyed at site if applicable. Receipt, usage and return must be documented on the respective forms. Reasons for any discrepancies must be thoroughly documented.

For storage conditions refer to the locally approved medication label and the STORM (Storage conditions for Trial Medications) document in the ISF.

Detailed instructions for the preparation and/or reconstitution of the dabigatran (when applicable) and for dispensing and intake for dabigatran formulations (capsules, pellets and oral liquid formulation) will be placed in the ISF.

If the storage conditions are found to be outside the specified range, the local Clinical Monitor (CML) for the study should be contacted immediately and the medication should be quarantined in the IRT until further notice.

4.1.8 Drug accountability

Drug supplies, which will be provided by the sponsor, must be kept in a secure, limited access storage area under the storage conditions defined by the sponsor. A temperature log

Proprietary confidential information.

© 2019 Boehringer Ingelheim International GmbH or one or more of its affiliated companies. All rights reserved.

This document may not - in full or in part - be passed on, reproduced, published or otherwise used without prior written permission.

must be maintained to make certain that the drug supplies are stored at the correct temperature.

The investigator / pharmacist / investigational drug storage manager will receive the investigational drugs delivered by the sponsor when the following requirements are fulfilled:

- approval of the study protocol by the IRB / ethics committee,
- availability of a signed and dated clinical trial contract between the sponsor and the Head of Trial Centre,
- approval/notification of the regulatory authority, e.g. competent authority,
- availability of the curriculum vitae of the principal investigator,
- availability of a signed and dated clinical trial protocol or immediately imminent signing of the clinical trial protocol,
- if applicable, availability of the Form 1572.

The investigator / pharmacist / investigational drug storage manager must maintain records of the product's delivery to the trial site, the inventory at the site, the use by each patient, and the return to the sponsor or alternative disposition of unused medication.

These records will include dates, quantities, batch/serial numbers, expiry ('use by') dates, and the unique code numbers assigned to the investigational product and trial patients. The investigator / pharmacist / investigational drug storage manager will maintain records that document adequately that the patients were provided the doses specified by the CTP and reconcile all investigational product received from the sponsor. At the time of return to the sponsor / appointed CRO, the investigator / pharmacist / investigational drug storage manager must verify that all unused or partially used drug supplies have been returned by the clinical trial patient and that no remaining supplies are in the investigator's possession.

4.2 CONCOMITANT THERAPY, RESTRICTIONS, AND RESCUE TREATMENT

Any additional drugs considered necessary for the patient's welfare may be given at the discretion of the investigator and with due consideration of the information provided in this protocol and the IB.

Details of concomitant medication administered to the patient during the course of the study should be recorded in the eCRF. This includes all concomitant therapies from time of patient randomisation until the patient completes follow up. In addition, at the randomisation visit, information regarding specific drugs (e.g. antithrombotic medication, medications with a potential drug-drug interaction with dabigatran etexilate (P-glycoprotein inhibitors and inducers)), administered in the 14 days prior to informed consent until time of randomisation and any medication given to directly treat an adverse event during the screening period will be recorded.

Certain concomitant therapies or surgery/intervention may require the temporary discontinuation of SOC or dabigatran etexilate. Study medication should be restarted as soon as safely possible.

Proprietary confidential information.

© 2019 Boehringer Ingelheim International GmbH or one or more of its affiliated companies. All rights reserved.

This document may not - in full or in part - be passed on, reproduced, published or otherwise used without prior written permission.

At the screening visit, the site must document details of the initial parenteral anticoagulant therapy given for the treatment of the VTE.

4.2.1 Rescue medication, emergency procedures, and additional treatment

The investigator is responsible for ensuring that procedures and expertise are available to cope with medical emergencies during the study (also refer to [Section 5.2](#)).

Major bleeds for patients on dabigatran:

If a patient experiences a major bleed, dabigatran should be stopped and the source of bleeding investigated and treated. This will generally involve coagulation testing (e.g. activated partial thromboplastin time (aPTT), TT, ecarin clotting time (ECT), platelet count), and possibly transfusion, diagnostic procedures and/or surgical haemostasis.

There is currently no specific reversal agent commercially available to counteract the antithrombotic activity of dabigatran in children; however there is one in development ([P15-06362](#)). If a clinical study with specific reversal agent in paediatric patients is approved by the local health authority and ethic committees during the course of this study, instructions on how to use the specific reversal agent in appropriate cases or conditions and the requirements of participation in the respective clinical studies may be provided to the investigators. In such cases cross reporting of lab results might be applied in order to limit the blood volume required for analysis.

[figure not shown]
Since dabigatran is excreted predominantly by the renal route adequate diuresis must be maintained. Appropriate standard treatment, e.g. surgical haemostasis as indicated and volume replacement should be undertaken as appropriate. In addition, consideration may be given to the use of fresh frozen plasma ([P10-03790](#)). As protein binding is low, dabigatran is dialyzable, however there is limited clinical experience in this setting. Clearance of dabigatran by haemodialysis was investigated in patients with end-stage renal disease. Dialysis was conducted with 700 mL/min dialysate flow rate, four hour duration, a blood flow rate of either 200 mL/min or 350-390 mL/min. This resulted in a removal of 50% or 60% of free- or total dabigatran concentrations, respectively. The amount of drug cleared by dialysis is proportional to the blood flow rate. There is some experimental evidence to support the role of agents such as activated prothrombin complex concentrates (APCC, e.g. FEIBA), recombinant Factor VIIa and three or four factor concentrates (Factors II, IX and X with or without Factor VII) in reversing the anticoagulant activity of dabigatran. The usefulness in clinical settings has not yet been systematically demonstrated. Consideration should also be given to administration of platelet concentrates in cases where thrombocytopenia is present or long-acting antiplatelet drugs have been used. All symptomatic treatment has to be given according to the physician's judgment.

A summary of how to manage bleedings on dabigatran etexilate is outlined in [Figure 4.2.1: 1](#).

Proprietary confidential information.

© 2019 Boehringer Ingelheim International GmbH or one or more of its affiliated companies. All rights reserved.

This document may not - in full or in part - be passed on, reproduced, published or otherwise used without prior written permission.

¹ for bleeding definitions see [Section 5.1.2.3](#)

² when appropriate

³ recommendations based on limited clinical or non-clinical data only, limited or no experience in volunteers or patients

Figure 4.2.1: 1 Management of bleeding on dabigatran therapy ([P10-03790](#))

Dabigatran must be stopped if a major bleeding event is observed. The patient must be treated and stabilized. Thereafter, the patient should be given SOC per investigator judgment and followed until the end of the trial based on the [Flow Chart](#) visit schedule.

Major bleeds for patients on SOC:

The local product label and local treatment guidelines should be followed in case a major bleed is observed with a LMWH or a VKA or fondaparinux. For major bleeding under LMWH therapy, protamine sulphate will reverse about 75% of the effects of LMWH. With VKA, treatment should be temporarily stopped and the anticoagulant effect reversed with vitamin K, prothrombin complex concentrates and/or fresh frozen plasma. Readministration of SOC, after the bleeding has been resolved and haemostasis has been achieved, is at the discretion of the investigator.

Clinically relevant non-major bleeds or minor bleeds:

If a patient experiences a clinically relevant non-major bleed or minor bleed, dabigatran or SOC may be continued, temporarily interrupted or permanently discontinued, at the discretion of the investigator. It is not a requirement; however, that study drug is stopped in these cases.

Proprietary confidential information.

© 2019 Boehringer Ingelheim International GmbH or one or more of its affiliated companies. All rights reserved.

This document may not - in full or in part - be passed on, reproduced, published or otherwise used without prior written permission.

Management of dabigatran and SOC prior to and after planned surgery:

Dabigatran Treatment Discontinuation for Elective Surgical Interventions

For minor surgery or interventions with a low risk for bleeding per investigator judgment, elective procedures could take place 36 hours after the last dabigatran intake (two missed doses). Treatment can restart at investigator's discretion but not earlier than 2 days after minor surgical interventions.

For major surgery with high risk for bleeding per investigator judgment, interventions could take place at least 72 hours after the last dabigatran intake (5 missed doses). The decision to re-start treatment with dabigatran is at the investigator's discretion but should not occur prior to 7 days after major surgery. Patients should not re-start treatment with dabigatran after major surgery if there is a persistent increased risk of bleeding. The choice of alternative treatment is at the investigator's discretion. For minor procedures involving a critical organ such as lumbar or epidural punctures, interventions could only take place at least 72 hours after the last dabigatran intake (5 missed doses). The decision to re-start treatment with dabigatran is at the investigator's discretion but should not occur prior to 3 days after intervention.

The decision to use bridging therapy by UFH / LMWH during the peri-procedural period is left to the investigator's discretion and would depend on the bleeding risk and the thrombotic risk in each patient.

Dabigatran Treatment discontinuation for Acute Surgical Interventions

If urgent surgery/acute intervention is required, dabigatran etexilate should be temporarily discontinued. The surgery/intervention should be delayed at least 12 hours if possible after the last dabigatran dose. If surgery cannot be delayed there may be an increased risk of bleeding. The risk of bleeding should be weighed together with the urgency of the intervention. Local haemostasis and supportive care should be used during and after surgical intervention. If a dabigatran specific reversal agent becomes available in a framework of clinical investigation during the conduct of this study and the patient fulfils the criteria for inclusion, it could be proposed to patients who require urgent reversal of dabigatran effects.

SOC Treatment discontinuation for Elective and Acute Surgical Interventions

Local treatment guidelines should be followed for discontinuation and reintroduction of SOC in cases of planned or emergency surgery.

